6.1. Appendix 1 Study Population Analyses.....	18
6.1.1. Participant Disposition	18
6.1.2. Demographic and Baseline Characteristics.....	18
6.1.3. Protocol Deviations.....	19
6.1.4. Prior and Concomitant Medications	19
6.1.5. Prior Medical Condition and Disease Characteristics	19
6.2. Appendix 2 Data Derivations Rule	21
6.2.1. Criteria for Potential Clinical Importance	21
6.2.2. Study Period	21
6.2.3. Study Day and Reference Dates.....	22

6.2.4. Assessment Window	23
6.2.5. Multiple measurements at One Analysis Time Point	23
6.2.6. Handling of Partial Dates	23
Trademarks	25
7. REFERENCES.....	26

Version history

SAP Version	Approval Date	Protocol Version (Date) on which SAP is Based	Change	Rationale
RAP V3	08 Mar 2021	04	Not Applicable	Original version
SAP amendment 1	Refer Document Date	05	
1. Analysis and reporting of part 2 have been omitted.
 
2. List of TLF's are reduced just to support closure activities.
 
3. The term "Sub-study" is changed to "Arm"
 
4. Owing to the study termination the study team has collectively decided not to analyse data for the following endpoints: PK
	The study is getting terminated in part 1.

1. INTRODUCTION

The purpose of this SAP is to describe the planned final analyses and outputs for arm 3 in the Clinical Study Report (CSR) for 205801.

1.1. Objectives, Estimands and Endpoints

Part 1:

Objectives	Endpoints
Primary Objectives	Primary Endpoints

To determine the safety and tolerability of novel regimens	
AEs, SAEs, DLTs, changes in safety/laboratory assessment parameters, dose modifications
Secondary Objectives	Secondary Endpoints

To provide a preliminary evaluation of the efficacy of feladilimab in combination with novel regimensCharacterize the pharmacokinetic properties of feladilimab (ICOS Agonist) or investigational feladilimab combination partners	
Objective Response Rate (ORR)Disease Control Rate (DCR)PK parameters that include Cmax and Cmin for feladilimab and in combination (and investigational agent/s included in other arms), as data permit.
Exploratory Objectives CC1	Exploratory Endpoints

1.2. Study Design

Overview of Study Design and Key Features	

Advanced NSCLC progressed on prior PD(L)1 & platinum chemo Stratify by squamous vs non-squamous Line of PD(L)1 therapy 1st vs. 2nd
 
Part 1: safety, PK/PD n = 10-15 per combination
 
Part 2: Survival
 
* Decision on each combination to proceed will be conditional on criteria from Section 5.1 and 10.5.1.1.
 
The two study populations (Part 1 and 2) are separate and distinct. Data from Part 1 and 2 will not be combined.
	
Between 10-20% of newly enrolled participants in subsequent substudies (depending upon the number of experimental arm trial) will be randomized to SoC once the initial 35 participants have been enrolled on control.
 
* Decision on each combination to proceed will be conditional on criteria from Section 5.1 and 10.5.1.1.
 
The two study populations (Part 1 and 2) are separate and distinct. Data from Part 1 and 2 will not be combined.

Design Features
 
 • A randomized, open-label, platform trial utilizing a master protocol • The study has 2 parts, i.e. part 1 and part 2. • Part 1 is a non-randomized part based on safety and pharmacokinetics/pharmacodynamics (PK/PD) evaluation. Part 2 is a randomized part, comparing the efficacy and safety of these novel regimens with SoC. • If the study passes part 1, then the participants will be recruited for part 2. • The final analysis for part 1 will be performed once all the participants complete 2 post baseline tumour assessments. • For part 2, interim analysis will be performed once 45 death events (18 in combination arm) are observed in the study. The primary analysis will be performed when 75 events are observed, and final analysis will be performed when 85 events are observed. • Arm 3 is getting terminated in part 1. 
Study intervention
 
 • The study will evaluate the safety and efficacy of feladilimab (ICOS agonist) in combination with ipilimumab. • There is no dose escalation in part 1, but the safety will be evaluated based on mTPI process • Combination study treatment will continue to be administered at the indicated schedule for a maximum duration of approximately 2 years or up to 35 treatment visits whichever comes first, or until disease progression as determined by iRECIST, death, unacceptable toxicity, or other protocol-defined criteria are met. 	

Overview of Study Design and Key Features						
		Treatment Arm	Dosage	Route of Administration	Dosing Frequency	
		Feladilimab	24 mg	IV infusion	Once Q3W	
		Ipilimumab	1 mg/kg or 3 mg/kg	IV infusion	Once Q3W	
Study intervention Assignment	
 In part 1, participants will be assigned to either 1mg/kg or 3mg/kg ipilimumab cohort depending on study team's decision. 					
Interim Analysis	
 No interim analysis will be performed in part 1. 					

2. STATISTICAL HYPOTHESES

Part 1: The primary objective of Part 1 is to establish the safety and tolerability of the experimental combination regimen of each arm.

2.1. Multiplicity Adjustment

No multiplicity adjustment is needed for part 1 analysis

3. ANALYSIS SETS

Population	Definition / Criteria	Analyses Evaluated
Screened	
 • All participants who were screened for eligibility. 	
 • Study Population
Safety	
 • All randomized participants who received at least one dose of SoC or experimental regimen based on actual treatment received. 	
 • Safety
Intent-To-Treat (ITT)	
 • All participants who were randomized to treatment regardless of whether the participants actually received study treatment. 	
 • Study Population • Efficacy
DLT Evaluable	
 • A subset of participants in part 1 who have received the first course of treatment containing both agents within an arm and followed up for a 21-day period or withdrawn within 21 days due to an AE meeting the definition of a DLT. • For oral dosing, a participant is considered DLT evaluable if they received at least 80% the first course of treatment containing both agents within an arm 	
 • DLT

Population	Definition / Criteria	Analyses Evaluated
	and followed up for a 21-day period or withdrawn within 21 days due to an AE meeting the definition of a DLT	

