4. STATISTICAL ANALYSES

4.1. General Considerations

4.1.1. General Methodology

Safety analysis set will be used for all study population analyses, safety analyses, and efficacy analyses.

Confidence intervals will use 95% confidence levels unless otherwise specified.

Unless otherwise specified, continuous data will be summarized using descriptive statistics: n, mean, standard deviation (std), median, minimum and maximum. Categorical data will be summarized as the number and percentage of participants in each category.

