4.2. Primary Endpoint(s) Analyses

The primary endpoint is DLT rate, AE's and SAE's. The analysis and reporting of AE's and SAE's are discussed in Section 4.5.

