4.2.1. Definition of DLT

A DLT is defined as an AE that meets at least one of the criteria listed in protocol and is considered by the investigator to be clinically relevant and attributed (probably or possibly) to the study treatment during the 21-day DLT observation period.

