4.2.2. Main analytical approach

A listing of adverse events recorded as dose-limiting toxicities during the determinative period will be provided. Additionally, a summary of the number of patients experiencing DLTs will also be provided.

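### The DLT Evaluable definition can exclude a participant because of the DLT itself, when a DLT on the first agent prevents the second, which lowers the reported DLT rate

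*SAP*

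**What the plan says.** Section 4.2 of the SAP states: "The primary endpoint is DLT rate, AE's and SAE's". Section 3 assigns a DLT Evaluable set to the DLT analysis. Its members are Part 1 participants who "received the first course of treatment containing both agents within an arm and followed up for a 21-day period or withdrawn within 21 days", where the withdrawal must be for an adverse event that meets the DLT definition. A parallel bullet for oral dosing has the same structure and replaces full receipt with "received at least 80% the first course of treatment containing both agents within an arm".

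Section 4.2.1 defines the event. It must meet a protocol criterion, be judged clinically relevant by the investigator, and be "attributed (probably or possibly) to the study treatment during the 21-day DLT observation period". Receipt of both agents is not a condition.

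Section 4.2.2 plans the displays: "A listing of adverse events recorded as dose-limiting toxicities during the determinative period will be provided", and in addition "a summary of the number of patients experiencing DLTs will also be provided". It names no analysis set and no denominator. Section 4.1.1 gives the general rule: "Safety analysis set will be used for all study population analyses, safety analyses, and efficacy analyses".

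**The concern.** An evaluability rule that removes DLT-free participants who never had the combination is reasonable, because their record says little about its tolerability. A rule that removes a participant because the outcome occurred is a different matter. If a qualifying event on the first agent is the reason the second is not given, the event causes its own exclusion. The exclusion is then informative and acts in one direction only: it takes one from the numerator and one from the denominator, which lowers the rate.

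At stake is the DLT rate in the study report for arm 3. Section 5 caps enrolment at 15 per ipilimumab dose level, so one participant moves the rate by several percentage points.

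**Working it through.** **Step 1: the logic of the set.** Let A = received the first course with both agents, B = followed for 21 days, C = "withdrawn within 21 days due to an AE meeting the definition of a DLT". The sentence reads A and B or C, with no punctuation or list structure to fix the grouping.

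- Reading 1, A and (B or C). Follow-up and withdrawal are paired alternatives, and receipt of both agents governs both. This is the more natural reading: exposure is stated first, and the oral-dosing bullet follows the same order.
- Reading 2, (A and B) or C. Withdrawal for a DLT qualifies on its own.

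**Step 2: apply both readings to participants with a DLT under Section 4.2.1.**

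| Participant with a DLT within 21 days | A | B | C | Reading 1 | Reading 2 |
|---|---|---|---|---|---|
| Both agents given, stays in follow-up | yes | yes | no | evaluable | evaluable |
| Both agents given, withdrawn for the DLT | yes | no | yes | evaluable | evaluable |
| Second agent not given, withdrawn for the DLT | no | no | yes | **excluded** | evaluable |
| Second agent not given, stays in follow-up | no | yes | no | **excluded** | **excluded** |

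The third row depends on the reading; the fourth does not. The SAP does not say whether withdrawal here means from treatment or from the study, although Section 4.5.3.2 lists the two separately. If it means treatment, Reading 2 would also keep a participant in the fourth row who stopped treatment permanently. It would still not keep one who missed only the second agent of the first course.

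**Step 3: size.** The SAP states no Part 1 DLT rate, power or operating characteristics, so there is no plan figure to reproduce. For n participants with x DLTs, one of which is excluded:

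change = x/n − (x−1)/(n−1) = (n−x)/[n(n−1)], which is positive whenever x < n.

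Inputs: n = 15 is the maximum per dose level in Section 5, and n = 10 is the lower end of the Part 1 range in Section 1.2. The values of x are assumptions.

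| Kept | Excluded | Fall |
|---|---|---|
| 1/15 = 6.7% | 0/14 = 0% | 14/210 = 6.7 points |
| 3/15 = 20.0% | 2/14 = 14.3% | 12/210 = 5.7 points |
| 1/10 = 10.0% | 0/9 = 0% | 9/90 = 10.0 points |
| 3/10 = 30.0% | 2/9 = 22.2% | 7/90 = 7.8 points |

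For x from 1 to 5 the fall is 4.8 to 6.7 points at n = 15 and 5.6 to 10.0 points at n = 10. For scale, the exact 95% interval is 4.3 to 48.1% for 3/15 and 1.8 to 42.8% for 2/14. The shift is small against sampling error, but it is systematic.

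**Step 4: sensitivity to frequency.** If the true rate is p and a share f of participants with a DLT is excluded, the expected rate is approximately p(1−f)/(1−pf). For an assumed p = 30%:

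- f = 10%: 0.270/0.970 = 27.8%
- f = 25%: 0.225/0.925 = 24.3%
- f = 50%: 0.150/0.850 = 17.6%
- f = 0: no change

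The SAP gives no infusion order or interval, so f cannot be estimated from it.

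**The case against.** The strongest reply is that the sentence does not have to be read strictly. Under Reading 2 a participant withdrawn for a DLT on the first agent is kept, so it cannot be said that the plan plainly requires both agents of everyone with a DLT. That stands for the withdrawn participant. It does not help the participant who stays in follow-up.

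A second reply is that an event definition and an evaluable set do different jobs, and that a rate meant to describe a combination may carry an exposure condition. That is fair for DLT-free participants. For participants with a DLT it would be a deliberate choice to exclude on outcome, and the SAP neither states nor justifies one.

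Third, a reader might infer that the DLT disappears from the whole primary safety endpoint. The SAP does not support this. AEs and SAEs are part of that endpoint and are analysed on the Safety population (Section 4.5), whose exposure condition is a single dose. All AEs are listed. Even loss from the DLT display is not certain: Section 4.2.2 names no set, Section 4.1.1 points to the Safety set, and Section 3 points to DLT Evaluable. The specific assignment in Section 3 is the likelier one, since the set would otherwise have no use, but a programmer would have to choose.

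Fourth, a reader might infer that the mTPI evaluation is biased towards calling a dose level tolerable. The SAP mentions mTPI but gives no rules for it and no set on which it runs. This amendment serves the closing of an arm terminated in Part 1, so that consequence cannot be shown.

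**Conclusion.** The point holds as a defect of wording that permits exclusion on outcome. Under both readings, a participant with a DLT on the first agent who never receives the second and is not withdrawn falls outside the set assigned to the DLT analysis. Under the more natural reading, a withdrawn participant falls outside as well. Any such loss lowers the DLT-rate component of the primary endpoint, by roughly 5 to 10 percentage points per case at 10 to 15 participants with 1 to 5 DLTs.

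This rests on three assumptions: the DLT summary uses the DLT Evaluable set, the agents are given in sequence, and at least one such case occurs. The SAP settles none of them. The effect is confined to the DLT rate; the event remains visible in the AE and SAE outputs. It should be corrected because the direction of error is known and the correction costs almost nothing.

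**What to change.** In Section 3, define DLT Evaluable as Part 1 participants who either:

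- (a) received any study treatment and had an adverse event meeting the DLT definition within the 21-day period, whether or not both agents were given and whether or not the participant was withdrawn; or
- (b) received the first course of both agents (at least 80% of it for oral dosing) and were followed for 21 days without a DLT.

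In Section 4.2.2, state that the DLT summary uses this set as its denominator, as an exception to the Safety-set rule in Section 4.1.1. In the DLT listing already planned, flag any DLT that occurred before the second agent was given.

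The cost is a short rewording and one listing variable. The downside is that a DLT on one agent alone counts in the combination rate; the flag discloses this, and a reader can recompute the rate without it.

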5. SAMPLE SIZE DETERMINATION

Part 1:

A maximum of 15 participants will be enrolled to each scheduled dose level of ipilimumab in Part 1.

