6.1.1. Participant Disposition

A summary of the number of subjects in each of the analysis sets described in Section 3 will be provided. Number of subjects based on the Safety will be summarized by country and site for each dose level.

A summary of subject status and reason for study withdrawal will be provided. This display will show the number and percentage of subjects who have completed the study or have withdrawn from the study, including primary and secondary (if any) reasons for study withdrawal. Reasons for study withdrawal will be presented in the order they are displayed in the eCRF (Electronic Case Report Form). Subjects who die for any reason during on-treatment period will be considered to have completed the study.

A summary of study treatment status will be provided. This display will show the number and percentage of subjects who discontinued study treatment and a summary of the primary reasons for discontinuation of study treatment. Reasons for study treatment discontinuation will be presented in the order they are displayed in the eCRF.

A listing of treatment discontinuation will be generated. The listing will include last dose date and primary reasons for study treatment discontinuation.

The number of subjects will be summarized by Country, Site ID and Investigator ID. This summary must be produced based on the safety population. The total column, summarizing subjects regardless of treatment, should always be included. Rows should be sorted alphabetically by country, then in numerical order by Site ID

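### The DLT Evaluable set tests why a participant left early, not whether a DLT occurred, so a participant with a DLT who leaves before day 21 for another reason drops out of the DLT rate

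*SAP*

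**What the plan says.** The DLT Evaluable row of SAP section 3 sets two conditions. The participant must have received the first course containing both agents, and must then have been "followed up for a 21-day period or withdrawn within 21 days due to an AE meeting the definition of a DLT". The second bullet, for oral dosing, changes the exposure condition but repeats the same two follow-up routes. The row assigns the DLT analysis to this set.

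Section 4.2.1 defines a DLT as an AE that meets protocol criteria, is judged clinically relevant, is attributed to study treatment and falls in the 21-day observation period. Leaving the study or stopping treatment is not part of that definition.

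Section 4.2 states: "The primary endpoint is DLT rate, AE's and SAE's". Section 4.2.2 plans a listing of DLTs and says that "a summary of the number of patients experiencing DLTs will also be provided". Section 4.1.1 adds the general rule that "Categorical data will be summarized as the number and percentage of participants in each category".

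On size, section 1.2 gives "n = 10-15 per combination", and section 5 says: "A maximum of 15 participants will be enrolled to each scheduled dose level of ipilimumab in Part 1".

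**The concern.** An evaluable set for DLTs normally has two jobs. It keeps everyone who had the event in the window, because their outcome is known. It also keeps those without the event who were watched long enough for its absence to mean something. A participant without a DLT who leaves early is uninformative and is properly left out.

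Section 3 does the second job but not all of the first. A participant whose follow-up ends early is admitted only when the DLT was the reason for leaving. Someone who had a DLT and left early for a different reason has a known outcome, yet the rule treats that person like someone whose outcome is unknown.

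At stake is the DLT rate of Part 1. In cohorts this small, one misplaced participant can turn a non-zero rate into zero, and the error runs in the favourable direction.

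**Working it through.** **1. The two definitions side by side.** Each case below assumes that the first-course condition is met.

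| Case | DLT under 4.2.1? | 21 days of follow-up? | Withdrawn because of the DLT? | In the set under section 3? |
|---|---|---|---|---|
| DLT, followed for 21 days | Yes | Yes | Not needed | Yes |
| DLT on day 8, withdrawn because of it | Yes | No | Yes | Yes |
| DLT on day 8, consent withdrawn on day 15 for another reason | Yes | No | No | **No** |
| DLT on day 8, lost to follow-up or dead from another cause on day 15 | Yes | No | No | **No** |
| Fatal DLT on day 15 | Yes | No | Unclear | **Unclear** |
| No DLT, leaves on day 15 | No | No | No | No (appropriate) |

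The third and fourth rows carry the finding. The days are illustrative.

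**2. Direction of the error.** Let x be the number of participants with a DLT and n the number who should be evaluable. Removing one participant with a DLT changes x/n to (x − 1)/(n − 1). The fall is

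x/n − (x − 1)/(n − 1) = (n − x) / [n(n − 1)].

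This is positive whenever x < n and zero only when x = n. The rate can never be pushed up.

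**3. Size.** The SAP states no expected DLT rate, so there is no figure of its own to reproduce, and the counts x are assumed. The values of n are 15 (the cap per dose level in section 5) and 10 (the lower per-combination figure in section 1.2). One participant with a DLT is excluded, and all others complete 21 days.

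| n | x | Counted | Excluded | Fall, percentage points |
|---|---|---|---|---|
| 15 | 1 | 1/15 = 6.7% | 0/14 = 0% | 14/(15×14) = 6.7 |
| 15 | 2 | 2/15 = 13.3% | 1/14 = 7.1% | 13/(15×14) = 6.2 |
| 15 | 3 | 3/15 = 20.0% | 2/14 = 14.3% | 12/(15×14) = 5.7 |
| 10 | 1 | 1/10 = 10.0% | 0/9 = 0% | 9/(10×9) = 10.0 |
| 10 | 2 | 2/10 = 20.0% | 1/9 = 11.1% | 8/(10×9) = 8.9 |
| 10 | 3 | 3/10 = 30.0% | 2/9 = 22.2% | 7/(10×9) = 7.8 |

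For scale, the exact (Clopper-Pearson) 95% interval is 0.2 to 31.9% for 1/15 and 0 to 23.2% for 0/14. The SAP plans no interval for the DLT rate. These only show that the shift lies well inside the sampling uncertainty of such a cohort.

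**The case against.** The strongest reply is that the case is rare and visible. It needs a DLT and an unrelated early exit in the same participant within 21 days, and the SAP gives no rate for either. The DLT listing does not depend on evaluability, and AEs, SAEs and deaths are reported separately, so a reader could find the event. All of this stands and keeps the point minor. It does not repair the rule, because the rate would then disagree with the plan's own listing.

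A second reply is that the protocol, which is not at hand, may define evaluability differently. That is possible. But section 4.2.1 sends the reader to the protocol for the DLT criteria, while section 3 states the evaluability rule in full, so the stated rule is the one a programmer would apply.

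Three stronger readings are tempting and are not supported:

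- **That fatal DLTs are certainly excluded.** Section 6.1.1 says: "Subjects who die for any reason during on-treatment period will be considered to have completed the study". A reader might infer that a death is therefore never a withdrawal. But that sentence governs a disposition display, not membership of an analysis set. Section 6.2.2.1 also has two on-treatment windows, one ending at treatment stop and one 30 days later, so an early death may not even fall under it. The ordinary reading of a fatal DLT is that participation ended because of that AE. The wording leaves the case open and no more.
- **That a dose or go/no-go decision is biased.** Section 1.2 says: "There is no dose escalation in part 1, but the safety will be evaluated based on mTPI process". The SAP gives no mTPI target, boundary or analysis, and its outputs are cut back to support closure of the study in Part 1. No decision can be shown to rest on this rate.
- **That two analysis sets contradict each other.** Section 4.1.1 names the Safety set for safety analyses in general, but section 3 assigns DLT specifically to the DLT Evaluable set. Section 4.2.2 does not repeat the set or give a denominator. That is a drafting matter.

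**Conclusion.** The definition is wrong as written, and the consequence is minor. A participant who meets the first-course condition, has a DLT and leaves before day 21 for an unrelated reason is excluded from the set used for a primary endpoint. A fatal DLT is ambiguous.

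The resulting error is downward only, apart from the limiting case where every evaluable participant has a DLT. For one such participant and one to three DLTs in all, it is about 6 to 7 percentage points at n = 15 and 8 to 10 points at n = 10. These figures rest on assumed DLT counts, on exactly one excluded case, and on the DLT summary being run on the DLT Evaluable set as section 3 directs. If no such case arose, the reported rate is unaffected.

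**What to change.** In section 3, add one sentence to each of the two DLT Evaluable bullets: a Part 1 participant who meets that bullet's first-course condition and has a DLT within the 21-day period is DLT evaluable whatever the later disposition, including death. The 21-day follow-up requirement then applies only to participants without a DLT. Reconcile the new wording with the protocol's evaluability definition so that the two documents select the same participants.

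The cost is a sentence in each bullet and one check against the protocol, with no new data or output. The only downside is that the reported DLT rate may be slightly higher than under the present wording.
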